### 9.4 Lost to Follow-up

All reasonable effort should be made to contact any subject lost to follow-up during the study to complete assessments and retrieve any outstanding data. If the subject is unreachable after three good faith attempts, **at a minimum, the Investigator should follow up with a registered letter requesting contact** so safety data may be collected, recorded, and reported (if necessary).

### 9.5 Stopping Rules

#### 9.5.1 Dose-Escalation Stopping Rule

Dose recommendations will be made by a DEC based upon a review of all available safety data, on a continuous basis as well as at discrete timepoints. Available data will be based on safety and pharmacodynamic evaluations including but not limited to, DLTs, AEs, TEAEs, SAEs, PD (including but not limited to IgG levels), and clinical outcomes.

Dose-limiting toxicity (DLT) will be defined generally as severe (Grade 3) AEs occurring in  $\geq 2$  subjects in any cohort that are determined to be clinically significant and considered related to study drug.

If 2 or more subjects at any time in any cohort have Grade 3 AEs that are determined to be clinically significant and considered to be related to study drug, dosing will be halted within that cohort and dose-escalation to a higher dose will not occur. Upon review of the available information, the DEC may reduce the dose prior to enrolling additional subjects using the guidelines below:

- Cohort 1: Dose may be reduced by at least 50%.
- Cohort 2: Dose may be reduced by at least 33%.
- Cohort 3: Dose may be reduced to a level lower than the Cohort 2 dose.
- Cohort 4 (optional cohort): Dose may be reduced to level lower than the Cohort 3 dose.

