	
Further, at any time during the study, the DEC may review all available safety data (including but not limited to DLTs, AEs, TEAEs, and SAEs), PD (including but not limited to IgG levels), and clinical outcomes.
 
 
• If 2 or more subjects at any time in any cohort have Grade 3 AEs that are determined to be clinically significant and considered to be related to study drug, dosing will be halted within that cohort and dose-escalation to a higher dose will not occur. Upon review of the available information, the DEC may reduce the dose prior to enrolling additional subjects using the guidelines below:                     
 
– Cohort 1: Dose may be reduced by at least 50%.
 
– Cohort 2: Dose may be reduced by at least 33%.
 
– Cohort 3: Dose may be reduced to a level lower than the Cohort 2 dose.
 
– Cohort 4 (optional cohort): Dose may be reduced to level lower than the Cohort 3 dose.
 
 
 
 
NOTE: DLT will be defined generally as severe (Grade 3) AEs occurring in <math>\geq 2</math> subjects that are determined to be clinically significant and considered related to study drug.
 
 
• If any subject at any time during the study experiences a life-threatening AE (Grade 4) that is related to study drug, further dosing in all enrolled subjects will be suspended until the DEC has evaluated the event and determined the appropriate course of action.
 
• At any time during the study, the study or any ongoing study cohort may be discontinued if the DEC determines that further drug exposure would pose an undue risk to subjects.
 
 
Additional information on the DEC’s responsibilities as they pertain to data review, dose selection, opening and closing a cohort, individual and study stopping recommendations is provided in Section 9 and the DEC charter.

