### **9.5.2 Study Stopping Rule**

If any subject experiences a life-threatening AE (Grade 4) that is considered to be related to study drug, any further dosing in all enrolled subjects will be suspended until the DEC has evaluated the event and determined the next appropriate course of action. At any time during the study, the study may be discontinued if the DEC determines that further drug exposure would pose an undue risk to subjects.

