#### **10.3.2 Management of Allergic or Infusion-Related Reactions**

As observed with all mAbs administered by IV infusion, infusion reactions to SYNT001 are possible. In general, infusion reactions to mAbs observed in human studies typically develop

[figure not shown]
within 30 minutes to 2 hours after the initiation of drug infusion, although symptoms may be delayed for up to 24 hours. These infusion reactions can occur with the first dose of a mAb and are generally mild in severity, although severe and even fatal reactions can occur.

Allergic and/or infusion-related reactions include hypersensitivity reactions and cytokine release syndromes. These reactions are experienced by subjects during or within hours of the infusion of mAb therapy. Symptoms can include flushing, alterations in heart rate and blood pressure, dyspnea, bronchospasm, back pain, fever, urticaria, edema, nausea, and all types of rashes. Anaphylaxis is recognized as a severe, life-threatening, generalized, or systemic reaction. This is a medical emergency characterized by rapidly developing life-threatening airway and/or breathing and/or circulation problems usually associated with skin or mucosal changes.

Management of Grade 1 infusion reactions include interrupting the infusion or decreasing the rate of infusion by 50% and observing. Symptoms may also be treated as needed with medications such as diphenhydramine, hydrocortisone, or acetaminophen, either alone or in combination, depending on the subject's signs and symptoms. If the infusion is interrupted or the infusion rate is decreased, it is important to note that all study drug infusions must be completed within 4 hours of SYNT001 preparation.

[figure not shown]
Management of Grade 2 and higher infusion reactions should include stopping the infusion of study drug. Continued treatment with SYNT001 is prohibited following Grade 2 or higher infusion reactions. See [Figure 2](#) and [Figure 3](#) for details on the management of Grade 2 and Grade 3 infusion reactions. Allergic or infusion-related reactions will be graded in severity and managed based on NCI CTCAE Version 4.03 (see [Table 9](#)).

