**Figure 2. Management of Moderate (Grade 2) Infusion Reactions**

**Figure 3. Management of Severe (Grade 3 or Higher) Infusion Reactions**

**Table 9. Grading and Management of Allergic or Infusion-Related Reactions**

Adverse Event	Grade				
	1	2	3	4	5
Infusion-related reaction	Mild transient reaction; infusion interruption not indicated; intervention not indicated	Therapy or infusion interruption indicated but responds promptly to symptomatic treatment (eg, antihistamines, NSAIDs, narcotics, IV fluids); prophylactic medications indicated for ≤24 hours	Prolonged (eg, not rapidly responsive to symptomatic medication and/or brief interruption of infusion); recurrence of symptoms following initial improvement, hospitalization indicated for clinical sequelae	Life-threatening consequences; urgent intervention required	Death
Allergic reaction	Transient flushing or rash, drug fever <38.0°C. Intervention not indicated	Therapy or infusion interruption indicated but responds promptly to symptomatic treatment (eg, antihistamines, NSAIDs, narcotics, IV fluids); prophylactic medications indicated for ≤24 hours	Prolonged (eg, not rapidly responsive to symptomatic medication and/or brief interruption of infusion); recurrence of symptoms following initial improvement, hospitalization indicated for clinical sequelae (eg, renal impairment, pulmonary infiltrates)	Life-threatening consequences; urgent intervention required	Death
Anaphylaxis	–	–	Symptomatic bronchospasm, with or without urticarial; parenteral intervention indicated; allergy-related edema/angioedema; hypotension	Life-threatening consequences; urgent intervention required	Death
Cytokine release syndrome	Mild reaction; infusion interruption not indicated; intervention not indicated	Therapy or infusion interruption indicated but responds promptly to symptomatic treatment (eg, antihistamines, NSAIDs, narcotics, IV fluids); prophylactic medications indicated for ≤24 hours	Prolonged (eg, not rapidly responsive to symptomatic medication and/or brief interruption of infusion); recurrence of symptoms following initial improvement, hospitalization indicated for clinical sequelae (eg, renal impairment, pulmonary infiltrates)	Life-threatening consequences; pressor or ventilator support indicated	Death

Abstracted from NCI CTCAE Version 4.03.

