### Grades

Grade refers to the severity of the AE. The CTCAE displays Grades 1 through 5 with unique clinical descriptions of severity for each AE based on this general guideline:

- Grade 1 Mild; asymptomatic or mild symptoms; clinical or diagnostic observations only; intervention not indicated.
- Grade 2 Moderate; minimal, local or noninvasive intervention indicated; limiting age-appropriate instrumental ADL\*.
- Grade 3 Severe or medically significant but not immediately life-threatening; hospitalization or prolongation of hospitalization indicated; disabling; limiting self care ADL\*\*.
- Grade 4 Life-threatening consequences; urgent intervention indicated.
- Grade 5 Death related to AE.

A Semi-colon indicates 'or' within the description of the grade.

A single dash (-) indicates a grade is not available.

Not all Grades are appropriate for all AEs. Therefore, some AEs are listed with fewer than five options for Grade selection.

### Grade 5

Grade 5 (Death) is not appropriate for some AEs and therefore is not an option.

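### The stopping rules name only Grade 3 and only Grade 4, so a related death triggers neither, and two related Grade 4 events do not bar dose escalation

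*Protocol*

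**What the plan says.** Two automatic rules operate above the level of the individual subject.

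- **Escalation rule (section 9.5.1).** "If 2 or more subjects at any time in any cohort have Grade 3 AEs that are determined to be clinically significant" and are judged related to study drug, dosing in that cohort is halted and the dose may not go up. The same section sets the toxicity definition: "Dose-limiting toxicity (DLT) will be defined generally as severe (Grade 3) AEs occurring in" two or more subjects, again clinically significant and related.
- **Study stopping rule (section 9.5.2).** "If any subject experiences a life-threatening AE (Grade 4) that is considered to be related to study drug", dosing of every enrolled subject is suspended until the DEC has evaluated the event and decided what to do.

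The study design part of the synopsis repeats all three statements: the same escalation rule, a DLT note ("DLT will be defined generally as severe (Grade 3) AEs occurring in" two or more subjects) and the Grade 4 rule ("If any subject at any time during the study experiences a life-threatening AE (Grade 4) that is related to study drug"). The wording is therefore consistent and not a slip in one place.

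Sections 10.1 and 10.2.1 grade adverse events on CTCAE 4.03. Appendix 1 gives death its own level on that scale: "Grade 5 Death related to AE".

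**The concern.** Neither rule says *or higher*, and neither names Grade 5. Followed to the letter, the rules become less strict as events become more severe. Two related Grade 3 events forbid a higher dose, but two related Grade 4 events do not. One related Grade 4 event stops dosing for everyone, but one related death does not.

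An automatic rule is there so that dosing stops before anyone has to exercise judgement. The only other mandatory rule, section 9.5.3, stops dosing in the affected subject alone, which protects nobody else after a death.

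The protocol itself contemplates the outcome that the rules omit. Section 2.2 reports one death in the 14-week monkey study, attributed to an infusion reaction. Section 10.3.2 warns that fatal infusion reactions can occur with monoclonal antibodies. Cohort 3 gives 14 weekly doses and needs no staggered start if its dose is no higher than one already given. Section 2.2 reports no serious or dose-limiting events in the healthy-volunteer study, so this concerns how the rule is written and not a known signal.

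**Working it through.** The plan gives no figure to reproduce. The check applies the two rules literally to every combination of worst related, clinically significant grade.

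**Inputs**
- Escalation bar (9.5.1 and synopsis): at least 2 subjects in a cohort with grade = 3.
- Suspension (9.5.2 and synopsis): at least 1 subject with grade = 4.
- Possible worst grades: 3, 4, 5 (Appendix 1).
- Revised thresholds: at least 2 subjects with grade ≥ 3 for the bar; at least 1 subject with grade ≥ 4 for the suspension.

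**One subject**

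| Worst grade | As written | Revised |
|---|---|---|
| 3 | neither | neither |
| 4 | suspension | suspension |
| 5 | neither | suspension |

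**Two subjects in one cohort** (3 like pairs + 3 unlike pairs = 6)

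| Pair | Bar, as written | Suspension, as written | Bar, revised | Suspension, revised |
|---|---|---|---|---|
| 3-3 | yes | no | yes | no |
| 3-4 | no | yes | yes | yes |
| 3-5 | no | no | yes | yes |
| 4-4 | no | yes | yes | yes |
| 4-5 | no | yes | yes | yes |
| 5-5 | no | no | yes | yes |

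As written, the bar covers 1 of 6 pairs, the suspension 3 of 6, and 2 of 6 (3-5 and 5-5) meet neither rule. Revised, the bar covers 6 of 6, the suspension 5 of 6, and none is left uncovered.

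These counts show which patterns the rules reach. They are not probabilities: the pairs are not equally likely, and no event rates are assumed.

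**Could the text be read more widely?** Three comparisons within the protocol bear on this.
- Section 10.3.2 writes thresholds out when it intends them: "Continued treatment with SYNT001 is prohibited following Grade 2 or higher infusion reactions", and the title of Figure 3 is "Management of Severe (Grade 3 or Higher) Infusion Reactions".
- Section 10.2.3 lists death and life-threatening events as separate seriousness criteria.
- In section 10.2.3.2, the sponsor's 7-day reporting duty names fatal events and life-threatening events side by side, so one term is not taken to include the other.

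**The case against.** Four points can be made in defence of the text.

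1. **Bare Grade 3 as shorthand.** Section 10.3.2 refers to the management of Grade 3 infusion reactions and points to a figure whose title covers Grade 3 and above. The protocol is therefore not uniform in writing thresholds out. This weakens the literal reading but does not remove it: Grade 4 has its own rule with a different consequence, so taking Grade 3 in section 9.5.1 to mean exactly that grade is natural.

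2. **Death as an outcome.** Section 10.2.3 treats death as the outcome of an event, and a fatal event puts the subject at immediate risk of death, so it could count as life-threatening. It may also have been Grade 4 before it was fatal. This is arguable, but section 9.5.2 ties the phrase to Grade 4, and the protocol separates the two terms elsewhere. A stopping rule should not depend on that argument.

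3. **The Grade 4 pairs already get the wider response.** One related Grade 4 event suspends dosing in the whole study, whereas the Grade 3 rule halts one cohort. This stands. For the 3-4 and 4-4 pairs, all that is missing is the mandatory bar on a higher dose once the DEC has completed its review.

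4. **The DEC would act anyway.** Each new cohort needs a DEC recommendation, safety review is continuous, deaths and serious events are reported within 24 hours, and the DEC or sponsor can stop the study. The toxicity definition is hedged as general, and a DEC charter (not shown) may say more. All of this limits the harm. But these powers are discretionary, the hedge qualifies the definition and not the operative escalation sentence, and a wider charter would still leave the protocol needing to agree with it.

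**Conclusion.** The concern holds. As written, a single related death triggers no automatic study-level or cohort-level rule, and the mandatory bar on escalation applies to two Grade 3 events but not to two Grade 4 events or to a Grade 3 with a Grade 4. This is a safety rule stated wrongly, not detail left for another document.

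The practical harm is bounded by the Grade 4 suspension and by the DEC's and sponsor's discretion, so this should be fixed but does not invalidate the design. The Grade 5 omission is the weightier part.

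The conclusion rests on a literal reading of the named grades and on classifying each subject by worst related grade. It does not depend on any assumed event rate.

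**What to change.** - **Section 9.5.1 and synopsis:** replace Grade 3 with *Grade 3 or higher* in the toxicity definition and in the two-or-more-subjects escalation rule (four edits).
- **Section 9.5.2 and synopsis:** replace the life-threatening (Grade 4) trigger with *life-threatening or fatal AE (Grade 4 or 5)* (two edits).

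Optionally, define a DLT per subject, as a related, clinically significant event of Grade 3 or higher, and keep the count of two or more subjects as the separate escalation rule. The correction does not depend on this.

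The cost is six short wording edits in a protocol amendment, plus alignment of the DEC charter if it repeats the wording. Sample size, visits and analyses do not change.

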### **9.5.2 Study Stopping Rule**

If any subject experiences a life-threatening AE (Grade 4) that is considered to be related to study drug, any further dosing in all enrolled subjects will be suspended until the DEC has evaluated the event and determined the next appropriate course of action. At any time during the study, the study may be discontinued if the DEC determines that further drug exposure would pose an undue risk to subjects.

### **9.5.3 Individual Stopping Rule**

Dosing for any individual subject will be discontinued (ie, no further study drug will be given to that subject) if the subject experiences any study drug-related SAE or any study drug-related non-serious AE that, in the judgement of the Investigator (following consultation with the Medical Monitor, if desired) suggest that it could be unsafe to administer further study drug to that subject.

Subjects who are withdrawn from this study due to an AE determined to be related to study drug are to be followed until there is:

- Resolution or stabilization of the AE determined to be related
- The subject is lost to follow-up
- The event is otherwise explained

If there is a persistent AE contributing to discontinuation that is determined to be related to SYNT001, subjects must be followed with appropriate medical management until resolution or stabilization. Refer to [Section 10](#) for more information.

## 10. EVALUATION OF SAFETY

### 10.1 Safety Parameters

Subjects will be monitored continuously throughout the treatment and follow-up period for AEs (acute, delayed, and/or cumulative), as well as for changes in clinical status. Parameters measure/assess safety include physical examinations, vital sign measurements (including pulse oximetry), clinical (safety) laboratory tests (hematology, serum chemistries, urinalysis), concomitant medication assessments, and ECG. Clinical and laboratory AEs will be graded using the NCI CTCAE; Version 4.03 (see [Appendix 1](#)).

### 10.2 Adverse Events

An AE is defined as any untoward medical occurrence in a clinical trial subject associated with the use of a drug, whether considered drug related or not. An AE can be an unfavorable and unintended sign (eg, an abnormal laboratory value finding), a symptom, or a disease temporally associated with the use of a drug, without judgment as to causality. An AE can arise from use of the drug (eg, use in combination with another drug) and from any route of administration, formulation or dose, including an overdose. An AE also includes, but is not limited to, any clinically significant worsening of a pre-existing condition. Examples include:

- Any sign, symptom, physical finding, or laboratory result that has worsened in nature, severity or frequency compared to baseline
- Reactions from an investigational drug, including those occurring because of an overdose, abuse of the study drug, withdrawal phenomena, sensitivity or toxicity
- Concurrent illness that was not present or worsens in nature, severity, or frequency compared to baseline
- Injury or accident
- Exacerbation of a pre-existing condition

Pregnancy is not considered an AE or SAE; however, any pregnancy complication(s) should be recorded as an AE(s) or SAE(s) (if applicable). Elective abortions without complications should not be regarded as AEs, unless they were therapeutic abortions. Hospitalization for normal delivery of a healthy newborn should not be considered an SAE. If a female subject becomes pregnant during the conduct of the study, the Investigator must notify the Sponsor according to the procedures provided in [Section 10.5.4](#).

Planned hospitalization admissions or surgical procedures for a condition known to exist before the subject signed the informed consent are not an AE and should be recorded as medical history. If the planned hospitalization or procedure is executed as planned and without complication, the record in the subject's medical history is considered complete. However, if the event/condition deteriorates in an unexpected manner during the study or following surgery, it must be reported as an AE according to the procedures provided in [Section 10.2.1](#).

### 10.2.1 Recording an Adverse Event

For data collection, all untoward events that occur after informed consent through the last study visit are to be recorded on eCRFs by the investigational site. All AEs are to be accurately recorded on the **Adverse Event** page of the subject's eCRF. The severity of each AE will be graded using the NCI CTCAE, Version 4.03 (see [Appendix 1](#)). The date of onset as well as the end date of the event should be recorded or the event should be entered as "ongoing". In addition, the method used to treat the AE and the outcome of the AE will be noted. The Investigator will assess the relationship of the event to study drug.

### 10.2.2 Assessment of Causality

A medically qualified Investigator must assess the relationship of any AE (including SAEs) to the use of the study drug, as related or not related, based on clinical judgment and using all available information. The causal relationship between the study medication and the AE will be assessed using one of the following categories:

**Not Related:** Factors consistent with an assessment of Not Related include:

- Temporal relationship is lacking (eg, the event did not occur within a reasonable time frame following administration of the study medication); or
- Other causative factors more likely explain the event (eg, a pre-existing condition, other concomitant treatments).

**Related:** Factors consistent with an assessment of Related include:

- There is a positive temporal relationship (eg, the event occurred within a reasonable time frame following administration of study medication); or
- The AE is more likely explained by the investigational product than by another cause (ie, the AE shows a pattern consistent with previous knowledge of the investigational product or the class of the investigational product)

### 10.2.3 Serious Adverse Events

*(Notify Medpace Safety within 24 hours; document on eCRF)*

The SAE definition and reporting requirements are in accordance with Title 21 Part Code of Federal Regulations (CFR) 312.32 and the Guidance for Industry and Investigators Safety Reporting Requirements for Investigational New Drug (INDs) and Bioavailability /Bioequivalence Studies.

An AE is considered "serious" if, in the view of either the Investigator or sponsor, it results in any of the following outcomes:

- **Death:** This includes any death that occurs while the subject is "on study" through the last study visit.

**Note:** Death is an outcome of an AE and not an AE. The event(s) that caused death (eg, illness, accident) is the SAE. Death due to any other cause(s) must also be reported as an outcome of the reportable SAE.

- **Life-threatening adverse drug event:** An AE or suspected adverse reaction is considered “life threatening” if, in the view of either the Investigator or Sponsor, its occurrence places the patient or subject at immediate risk of death. It does not include an AE or suspected adverse reaction that, had it occurred in a more severe form, might have caused death.
- **Inpatient hospitalization or prolongation of existing hospitalization:** an AE that requires admission to a hospital for medical and/or surgical intervention.
  - In the absence of an AE, the Investigator should not report hospitalization or prolongation of hospitalization as an SAE, as detailed in the following examples:
    - An elective or previously scheduled surgery for a pre-existing condition that has not deteriorated unexpectedly after initiation of treatment (eg, a previously scheduled ventral hernia repair)
    - Hospitalization or prolongation of hospitalization is needed for a procedure required by the protocol
    - Hospitalization or prolongation of hospitalization is part of routine procedure followed by study center
    - Hospitalization for survey visits, annual physicals, or planned observation
    - Hospitalization for observation with release within 24 hours (eg, an emergency room visit for hematuria that results in a diagnosis of cystitis and discharge to home on oral antibiotics)
- **Persistent or significant incapacity or substantial disruption of the ability to conduct normal life functions**
- **Congenital anomaly/birth defect**
- **Important medical event:** An event that may not result in death, be life threatening, or require hospitalization may be considered an SAE when, based upon appropriate medical judgment, it may jeopardize the subject and may require medical or surgical intervention to prevent one of the outcomes listed in this definition.

